11.3. Data Management Plan

Pre-Screening Phase

The local Principal Investigator, or designee, will prepare and maintain adequate and accurate subject case histories with observations and data pertinent to the study. Study-specific Case Report Forms (CRFs) will document inclusion/exclusion criteria assessment, results of pre-screening procedures (integrative subtype classification, Ki67 immunohistochemistry, eligibility for active umbrella sub-protocol, and if subject enrolled on active umbrella sub-protocol), and adverse events deemed to be caused by pre-screening procedures, should they occur. Case report forms will be entered in a secure REDCap database and will be maintained by the local Principal Investigator and study staff. All subjects will be registered in the OnCore database, allowing the Stanford SRC and independent DSMB to judge the aggregate accrual and stopping rules for the study respectively.

Tissue sections that remain at Stanford after completion of pre-screening procedures will be labeled with a unique anonymous identifier generated by study staff and linked to protected health information in the secure REDCap database. The unique anonymized identifier will be assigned sequentially and will not be linked in any way to the subject's identifying information.

Treatment Phase

11.3.1. Case Report Form

All data for this study will be collected on the electronic Case Report Form (eCRF) developed for that purpose. For this study, REDCap will be the eCRF. Sites will be suitably trained on the use of the eCRF and appropriate site personnel will be provided electronic signatures, as required.

All site entries will be made in a secured web site and monitoring delegates will review the record for completeness using risk-based monitoring. The site investigator or designee will make necessary eCRF corrections. The site investigator must authorize the corrections to the entered data on eCRF. Specific instructions on use of the EDC system and guidelines for data entry and correction will be provided to the sites.

11.3.2. Study files and subject source documents

Subject confidentiality is strictly held in trust by the participating investigators, research staff, the Sponsor and their designees. This confidentiality is extended to cover testing of biological samples in addition to the clinical information relating to subjects. Authorized representatives of the Sponsor may inspect all documents and records required to be maintained by the site investigator, including but not limited to, medical records (office, clinic or hospital) and pharmacy records for the subjects in this study. Any data, specimens, forms, reports, and other records that leave the site will be identified only by a subject identification number to maintain confidentiality.

The site investigator must maintain adequate and accurate records to enable the conduct of the study to be fully documented and the study data to be subsequently verified. These documents include Investigators' Study Files and original subject clinical source documents generated at the study site. The term "original" means the first recording of the data. The site investigator will ensure the site master files are maintained, including the study protocol and its amendments, IRB and regulatory approvals with associated correspondence, informed consents, study drug records, staff curriculum vitae, all correspondence, and other appropriate documents.

Subject clinical source documents may include, but are not limited to, subject hospital/clinic records, physicians' and nurses' notes, appointment books, laboratory reports, ECGs, radiographs, and consultant letters. The site investigator must assure that all original source documents are available to support monitoring activities.

All subjects will be reported at the time of consent to the coordinating site (Stanford) to be registered in the OnCore database, allowing the Stanford SRC and independent DSMB to judge the aggregate accrual and stopping rules for the study respectively.

11.4 Protocol Deviation

Protocol deviation is a general term and includes protocol exceptions, changes made to avoid immediate harm to subjects, and protocol violations. Protocol deviations can be either major or minor. Protocol deviation may include unplanned instances or protocol noncompliance. For

example, situations in which the clinical investigator failed to perform tests or assessments as required by the protocol or failures on the part of participants to complete scheduled visits as required by the protocol, would be considered deviations.

11.4.1. Definitions

Protocol deviation (PD) is any change, divergence, or departure from the study design or procedures defined in the study protocol, consent document, recruitment process, or study materials (eg. questionnaires) originally approved by the IRB. Two classifications are used; Major Deviation and Minor Deviation.

Major deviation is any deviation that significantly affects the quality or completeness of data or impacts a participant's safety, rights, or welfare. Major deviations are study-specific and are determined by the protocol.

Minor deviation is a deviation that does not meet the criteria for major, but still represents a change, divergence or departure from the study design or procedures and does not have impact on data integrity or the final outcome defined in the protocol.

11.4.2. Deviation Management

All deviations from all participating sites must be entered into OnCore within 3 calendar days from the deviation awareness date. Classification of deviation (major vs. minor) can be performed by site with the help of site investigator, protocol director, and/or the Clinical Coordinating Center (CCC). Any deviation, particularly if classified as major, may be reviewed additionally at the CCC to ensure that deviation is addressed and closed with an appropriate Corrective and Preventive Action (CAPA) plan or system. While this study does not grant protocol waivers, deviations intended to eliminate a hazard to participants or to protect the life or well-being of participants should be used when necessary (eg. in an emergency) and discussed with the CCC as early as possible if known ahead of time. Research team members may not implement any deviations or changes from the protocol without agreement by Protocol Director.

12. STATISTICAL CONSIDERATIONS

Treatment Phase

12.2. Interim Analysis and Stopping Rules

There will be ongoing safety monitoring with periodic safety assessments by the DSMB. There will also be two formal assessments by the DSMB upon certain events within each cohort.

1. For the purposes of the interim toxicity assessment, toxicity is defined as treatment-related SAEs Grade 3 or higher. Toxicity will be formally analyzed in each investigational therapy arm after 12 patients are randomized to investigational therapy. If at least 4 of the first 12 patients randomized to investigational therapy experience toxicity, the study will be stopped; in other words, the threshold for unacceptable toxicity is 30%. If the true toxicity rate is 30%, the probability of stopping is 28%. If the true toxicity rate is 40%, the probability of stopping is 56% and if the true toxicity rate is 20%, then probability of stopping is 7%.
2. If 2 or more subjects in any cohort have their surgery delayed past the scheduled day due to possibly-, probably- or definitely-related adverse effects, as assessed by the treating physician or local Principal Investigator, enrollment to that cohort of the study will be halted, and the trial data will be reviewed by the DSMB to determine whether permanent closure of that arm is appropriate. The occurrence of surgery delay must be documented in the study REDCap database within 24 hours, which will immediately notify the IND-holder and Data Coordinating Center.

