APPENDIX D: STUDY DETAILS SPECIFIC TO INTEGRATIVE SUBTYPE 2 & 6 TUMORS (COHORT 2 ZOTATIFIN) AND TYPICAL RISK (COHORT 3 ZOTATIFIN).....	48
14. REFERENCES CITED.....	79

PROTOCOL SYNOPSIS

TITLE	An Umbrella, Randomized, Controlled, Pre-Operative Trial Testing Integrative Subtype-Targeted Therapeutics in Estrogen Receptor-Positive, HER2-Negative Breast Cancer
STUDY PHASE	2
INDICATION	Estrogen receptor-positive (ER ⁺), HER2-negative (HER2 ⁻) breast cancer
STUDY POPULATION	
Patients with newly-diagnosed (stage I to IV) ER⁺, HER2⁻ breast cancer (BC), or in-breast recurrence of ER⁺, HER2⁻ BC (at least 6 months since last endocrine therapy), whose tumor size is ≥ 1 cm and has tumor marker of proliferation Ki67 $\geq 10\%$, and is of integrative subtype 1; 2; 6 or Typical Risk (3, 4, 7, 8).
 
Ki67 is a intracellular marker of tumor proliferation that is assessed by immunohistochemistry.

INVESTIGATIONAL PRODUCTS and DOSAGES	
Integrative subtype 1 (Cohort 1): Alpelisib tablets 250 mg/day by mouth
 
Integrative subtypes 2 and 6 (Cohort 2) and Typical Risk (Cohort 3): Zotatatin 0.10 mg/kg x 1 administered by IV

ACTIVE CONTROL AGENTS AND DOSAGES	
Cohort 1: Tamoxifen 20 mg/day by mouth (commercial supply)
 
Cohort 2 & 3: Fulvestrant, two 250 mg intramuscular (IM) injections on Day 1. Fulvestrant is considered a standard mediation in this study, and is supplied as an IND-exempt agent.

PRIMARY OBJECTIVE	To evaluate the efficacy of investigational agent compared with standard endocrine therapy in reducing digital pathology software-assessed Ki67 values (using QuPath) from baseline to on-treatment biopsy after an appendix-specific treatment duration (ie, 14 days).
SECONDARY OBJECTIVE	To evaluate the efficacy of investigational agent compared with standard endocrine therapy on the proportion of subjects with Ki67 $< 10\%$ after an appendix-specific treatment duration (ie, 14 days).
TREATMENT SUMMARY	Subjects will be pre-screened to assess eligibility for participation in the treatment phase of the trial. In the treatment phase, enrolled subjects will be randomly assigned to either the investigational agent arm or the standard endocrine therapy arm. All subjects will be instructed to take their assigned therapy based on a duration specified in their respective appendix assignment, with the last day of treatment being the day prior to their surgery or scheduled biopsy. They will then undergo an on-treatment biopsy or definitive surgery.

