D-1.2.1.6. Potential for drug interactions. Based on metabolism and nonclinical drug interaction studies, there is low potential for zotatifin to perpetrate a drug-drug interaction via modulation of drug transporter and/or CYP enzyme activity. Zotatifin could be a victim of a drug-drug interaction caused by co-administered CYP3A modulating (inhibitors or inducers) drugs; zotatifin is primarily a substrate for CYP3A4. Concomitant use of strong or moderate inhibitors or inducers of CYP3A4 ([Appendix D-B](#)) with zotatifin is not allowed per protocol.

D-1.2.1.7. Non-clinical experience. Preclinical efficacy studies using zotatifin showed significant in vitro tumor growth inhibition and regression across multiple solid tumor cancer models; in particular, in vitro cell line screens identified that cell lines harboring KRAS activating mutations and/or receptor tyrosine kinase amplification (eg, FGFR or HER2) are especially sensitive to zotatifin-mediated apoptosis. These observations were extended in vivo with mouse xenograft models including for RTK-dependent (eg, HER2 or FGFR) breast cancer. Further details are available in the Investigator's Brochure, which is included with the IRB submission.

D-1.2.1.8. Safety. Clinical experience with zotatifin to date includes 1 ongoing, first-in-human, phase 1-2, open-label, sequential-group, dose-escalation and cohort-expansion study evaluating the safety, PK, pharmacodynamics, and antitumor activity of zotatifin in patients with

selected advanced solid tumor malignancies (Study eFT226-0002). The maximum tolerated dose (MTD) has not yet been defined, and dose escalation is in progress.

Investigations of zotatifin in combination with fulvestrant continue to explore dose escalation starting at zotatifin 0.1 mg/kg administered IV every other week in 14-day cycles (Part 1b cohort). As of 13 February 2023, the planned 3 participants have been enrolled in this cohort and completed their DLT-period.

Dose-limiting toxicities

As of 12 August 2022, there was 1 DLT (grade 3 thrombocytopenia) in the 0.035 mg/kg/week cohort, and 2 DLTs (grade 3 anemia and grade 3 GI hemorrhage) in the 0.1 mg/kg 2 weeks on / 1 week off cohort. In the Part 1B cohort utilizing zotatifin 0.1 mg/kg every other week in 14-day cycles, the dose planned for this study, all 3 planned DLT-evaluable were enrolled as of 13 February 2023 with no DLTs observed during the reportable period.

Treatment-emergent adverse events

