Each cohort of the study will need to accrue approximately 3 subjects per quarter to accrue the planned 50 subjects in 4 years for each cohort. Subjects will be recruited to participate in this study from an anticipated 10-15 sites, including Stanford Cancer Center. Similar sites have successfully completed accrual to TRIO 030 ([NCT03004534](#)), a window-of-opportunity study of an androgen receptor inhibitor in 36 early-stage breast cancer subjects. Early accrual to this study was predominantly patients with ER⁺/HER2⁻ breast cancer (the study also had a triple-negative breast cancer cohort), and during their first quarter, 7 patients were accrued to this study. As the study population in the present trial is anticipated to be 8% of the overall population of patients with ER⁺/HER2⁻ breast cancer, it will be necessary to screen approximately 40 patients per quarter to enroll 3 subjects. Thus, 6 sites performing similarly in the aforementioned window-of-opportunity trial would complete accrual on schedule, and it is anticipated that a total of 10-15 sites, recognizing that not all will have equivalent accrual capacity, should enable adequate accrual.

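### The only formal boundary on the toxicity rate is applied per cohort, although Cohorts 2 and 3 give one regimen; a pooled first look at 12 patients would come earlier

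*Combined protocol and SAP*

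**What the plan says.** Section 12.2 introduces its rules at cohort level: "There will also be two formal assessments by the DSMB upon certain events within each cohort". For toxicity, defined as treatment-related SAEs of Grade 3 or higher, it says: "Toxicity will be formally analyzed in each investigational therapy arm after 12 patients are randomized to investigational therapy". The boundary is: "If at least 4 of the first 12 patients randomized to investigational therapy experience toxicity, the study will be stopped". The section gives stopping probabilities of 7%, 28% and 56% at true rates of 20%, 30% and 40%. A second rule halts a cohort's enrollment for DSMB review once two or more of its subjects have surgery delayed by related adverse effects.

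The synopsis assigns Cohorts 2 and 3 the same zotatifin dose, "0.10 mg/kg x 1 administered by IV", and the same Day 1 fulvestrant. Appendix D gives them one safety calendar (D-7) and one eligibility checklist (D-A), which separates them only by integrative subtype. On accrual, D-8.2 says: "Each cohort of the study will need to accrue approximately 3 subjects per quarter". On earlier experience with this dose every other week plus fulvestrant, D-1.2.1.8 says "all 3 planned DLT-evaluable were enrolled as of 13 February 2023 with no DLTs observed"; it also says that the maximum tolerated dose was not yet defined.

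The only planned pooling of the two cohorts is the exploratory Ki67 interaction model in D-8.1.

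**The concern.** A toxicity rule per investigational arm suits an umbrella trial in which each cohort tests a different drug. Cohorts 2 and 3 differ in tumour subtype, not in what patients receive, and nothing in the documents suggests that subtype changes toxicity. Each patient receives a single infusion, so a stopping rule protects only those not yet dosed. What matters is how many have been dosed when the rule first applies.

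Counting per cohort delays that point. Suppose 4 of the first 12 patients on the regimen have qualifying toxicity, 2 in each cohort. The written boundary is then met for the regimen, but each arm holds about 6 patients with 2 events, and no formal toxicity look takes place.

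**Working it through.** **Inputs.** Look at 12 and boundary of at least 4 (12.2); about 3 subjects per quarter per cohort (D-8.2); 1:1 allocation (synopsis).

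**1. The plan's accrual figure.** 3 per quarter × 16 quarters = 48, in line with the planned 50 in 4 years.

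**2. Timing with equal, concurrent accrual.**
- Zotatifin patients per cohort: 3 × 1/2 = 1.5 per quarter.
- Per-cohort look: 12 / 1.5 = 8 quarters = 2 years, with 12 + 12 = 24 exposed.
- Pooled look: 12 / (2 × 1.5) = 4 quarters = 1 year, with 12 exposed.

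**3. Sensitivity to unequal accrual (assumed; not in the documents).** If Cohort 3 accrues k times as fast as Cohort 2, its look comes at 12 / (1.5k) quarters, the total exposed is then 12 + 12/k, and the pooled 12 is reached at 12 / (1.5 + 1.5k) quarters.

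| k | First cohort look (years) | Exposed by then | Pooled 12 (years) |
|---|---|---|---|
| 1 | 2.0 | 24 | 1.0 |
| 1.5 | 1.33 | 20 | 0.80 |
| 2 | 1.0 | 18 | 0.67 |
| 3 | 0.67 | 16 | 0.50 |

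If instead Cohort 3 opens 2, 4 or 6 quarters after Cohort 2, then 21, 18 or 15 are exposed at Cohort 2's look at 2 years. The pooled 12 comes at 1.25, 1.5 or 1.75 years.

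**4. The plan's stopping probabilities.** P(X ≥ r), with X binomial(12, p):

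| True rate | Stated in 12.2 | r = 4 (as written) | r = 5 |
|---|---|---|---|
| 20% | 7% | 20.5% | 7.3% |
| 30% | 28% | 50.7% | 27.6% |
| 40% | 56% | 77.5% | 56.2% |

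The stated figures do not reproduce with the written boundary; they match at least 5 of 12. The effect of a pooled look is therefore shown both ways.

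**5. Effect of adding a pooled first look (equal accrual).** A stop at the pooled look leaves 12 exposed; otherwise 24 are exposed by the cohort looks. Mean exposure is 24 − 12 × P(X ≥ r).
- 40% true rate: 24 − 12 × 0.775 = 14.7 (r = 4); 24 − 12 × 0.562 = 17.3 (r = 5).
- 30% true rate: 24 − 12 × 0.507 = 17.9 (r = 4); 24 − 12 × 0.276 = 20.7 (r = 5).

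For the chance of any stop, the two cohort looks alone give 1 − (1 − P)². With the pooled look added, I took the first 12 as 6 from each cohort and summed the exact binomial terms.

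| True rate | r = 4: cohort looks only | r = 4: pooled look added | r = 5: cohort looks only | r = 5: pooled look added |
|---|---|---|---|---|
| 10% | 5.1% | 6.5% | 0.9% | 1.2% |
| 20% | 36.9% | 41.7% | 14.0% | 17.2% |
| 40% | 94.9% | 95.9% | 80.8% | 83.9% |

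**The case against.** The strongest reply is that safety does not wait for this look. Section 11.2 has the DSMB reviewing safety data continuously, with power to recommend stopping. Section 7.5 requires every SAE to be reported within 24 hours, and every event the toxicity rule counts is an SAE. The surgery-delay rule is a second numeric trigger and has no 12-patient wait. All of this stands. A reader might infer that zotatifin patients go unmonitored until 24 are treated, that half the safety information is discarded, or that the toxicity rule is the only numeric safety trigger; the documents support none of these. What remains is narrower: none of these safeguards is a pooled boundary on the toxicity rate. In the 2-and-2 example the four events would be known, but no defined criterion would apply to them.

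A reader might also take 3 of 12 in each cohort as a missed signal. It is not: 6/24 = 25% lies below the 30% that Section 12.2 names as its threshold.

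Nor is 24 patients a forecast. It is the maximum under equal, concurrent accrual. Section 2.1 puts typical-risk tumours at about 75% of ER-positive, HER2-negative disease, against about 5% plus 6% for subtypes 2 and 6 in D-1.1, so Cohort 3 could fill faster and the gain would shrink.

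The gain also depends on a high true rate. D-1.2.1.8 reports 5 subjects with possibly related SAEs, and Table D-1 heads its column N = 72: 5/72 is about 7% across all doses. At a rate that low the pooled look would rarely fire. That is fair, but a stopping boundary exists for rates higher than expected, and only 3 participants had received this dose every other week with fulvestrant.

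Finally, Section 12.4.2 treats each cohort as an independent trial. That statement justifies not adjusting efficacy tests for multiplicity. It gives no reason to split the safety sample for one regimen.

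**Conclusion.** The point holds as a design improvement. With both cohorts accruing at the planned rate, the first formal toxicity look comes at 2 years with up to 24 patients exposed, against 1 year and 12 patients if pooled. In each unequal or staggered scenario above the pooled look is still earlier, with 15 to 21 exposed at the first cohort look.

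The benefit is earlier timing, not more power: at a 40% true rate the chance of any stop rises only from 94.9% to 95.9% (at least 4 of 12) or from 80.8% to 83.9% (at least 5 of 12).

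The timing result rests on the D-8.2 accrual rate and 1:1 allocation and does not depend on the boundary. The exposure and stopping figures depend on which boundary is meant, which the documents leave in conflict, and on equal accrual.

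**What to change.** 1. Reconcile the Section 12.2 boundary with its stated probabilities. This review does not say which is intended.
2. Add to Section 12.2 and the DSMB charter that, for cohorts sharing one regimen (currently Cohorts 2 and 3), the reconciled boundary is first applied to the first 12 investigational patients pooled across those cohorts. Keep the per-cohort looks.
3. State the combined stopping probabilities for the pooled and cohort looks together.
4. Say whether a trigger in one cohort also stops the other cohort on the same regimen; the present wording, that the study stops, leaves this open.

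The cost is a few sentences and no new data. The downside is more stops when toxicity is below the threshold: at a 20% true rate the chance of any stop rises from about 37% to 42% (at least 4 of 12) or from about 14% to 17% (at least 5 of 12).

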11.2. Data and Safety Monitoring Plan

For this study, the Lead Principal Investigator (PI) and IND-holder will be responsible for the active oversight of the patient safety, including at the participating sites, including regular data review to determine any necessary changes to the study design or safety monitoring. These regular reviews will occur internally at Stanford on a monthly basis between study investigator and delegated clinical research staff. A monthly call with participating sites will be held to discuss enrollment, safety data, and other study matters. The Stanford PI/PD may delegate some of these aforementioned responsibilities to another entity, such as the CCC. Additionally, the Stanford Cancer Institute Data and Safety Monitoring Committee (DSMC) will provide support to the Stanford PI/PD on matters related to quality assurance monitoring, review of aggregated protocol deviations, and prompt reports submitted to the necessary regulatory authorities.

SCI DSMC, with the support from the CCC (if necessary) will conduct data monitoring for this study using risk-based monitoring. The Stanford Cancer Institute DSMC will also monitor Stanford sites per their routine protocol for Stanford investigator-sponsored trials.

An independent data safety and monitoring board (DSMB) has been established to ensure patient safety, assess protocol compliance, and monitor the progress of the study. The DSMB is made up of physician(s) with expertise in breast cancer and clinical trials as well as a statistician with experience in clinical trials. The DSMB will be supported by an independent statistician who will be a non-voting member of the board. Details of the composition, roles, responsibilities, and processes of the DSMB will be documented in the DSMB Charter. The DSMB will review safety data on an ongoing basis and may recommend stopping or amending the study based on safety findings. The DSMB will not be otherwise involved in the conduct of the study.

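### Rule 1 in Section 12.2 counts toxicities that cannot be undone, but states no trigger before the 12th investigational-arm patient; acting when the count is reached stops equally often and spares a small number of patients

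*Combined protocol and SAP*

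**What the plan says.** Rule 1 of Section 12.2 defines its event: "toxicity is defined as treatment-related SAEs Grade 3 or higher". It sets the time of the formal look: "Toxicity will be formally analyzed in each investigational therapy arm after 12 patients are randomized to investigational therapy". It then gives the boundary and the consequence: "If at least 4 of the first 12 patients randomized to investigational therapy experience toxicity, the study will be stopped". The same paragraph names 30% as the unacceptable rate and prints stopping probabilities of 7%, 28% and 56% at true rates of 20%, 30% and 40%.

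Before the 12th patient, Section 12.2 provides ongoing monitoring with periodic DSMB assessments. Section 11.2 says of the DSMB: "The DSMB will review safety data on an ongoing basis and may recommend stopping or amending the study based on safety findings". No toxicity count is attached to either. Section 11.2 also provides monthly internal review and a monthly call with sites, and Sections 7.5 and 7.5.1 require SAE reports within 24 hours.

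Rule 2 of Section 12.2 (surgery delay) works differently. Enrollment to the cohort halts when two related delays have occurred, and the DSMB then reviews.

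**The concern.** A count of events among the first 12 patients can only rise. If it reaches the boundary at patient 8, nothing that happens in patients 9 to 12 can change the answer to rule 1. The only formal toxicity analysis the plan names is nonetheless tied to the 12th randomization, and no sentence makes reaching the count a trigger.

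Zotatifin is given once, on Day 1 (Appendix D, D-5.1.1). What is at stake is therefore not continued dosing of patients already treated, but further patients being randomized and dosed after the plan's own criterion has been met. They are pre-operative patients. Appendix D (D-1.2.1.8) describes an agent whose maximum tolerated dose was not yet defined, with three patients reported at the planned combination dose and schedule. Waiting adds exposure without adding information for this decision.

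**Working it through.** **Inputs.** From Section 12.2: boundary r = 4 as written, a look at N = 12, and printed stopping probabilities of 7/28/56% at true rates p = 20/30/40%. From Section 12.1: 1:1 allocation. From Appendix D, D-8.2: "Each cohort of the study will need to accrue approximately 3 subjects per quarter to accrue the planned 50 subjects in 4 years". Patients are assumed independent with a common event rate.

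**Step 1: the plan's own figures.** With a single look at 12, P(stop) = P(X ≥ r), where X is binomial(12, p).

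| Boundary | p = 20% | p = 30% | p = 40% |
|---|---|---|---|
| Printed | 7% | 28% | 56% |
| r = 4 (as written) | 20.5% | 50.7% | 77.5% |
| r = 5 | 7.3% | 27.6% | 56.2% |

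The printed figures do not belong to the written boundary. They match five or more of 12 at all three rates. Both boundaries are carried forward below.

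**Step 2: acting when the count is reached.** The r-th event falls at patient n with probability C(n−1, r−1) p^r (1−p)^(n−r). Summed over n = r to 12, this gives 20.5/50.7/77.5% for r = 4 and 7.3/27.6/56.2% for r = 5, identical to Step 1. The equality is exact: r events among fewer than 12 patients guarantee at least r among the first 12, and the converse also holds.

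**Step 3: patients spared.** The expected saving over all outcomes, including no stop, is the sum over n of (12 − n) × P(r-th event at n). With a recognition lag of k further arm patients, 12 − n is replaced by 12 − min(12, n + k). The lag is an assumption; the documents give none.

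| Boundary | Lag | p = 20% | p = 30% | p = 40% |
|---|---|---|---|---|
| 4 | 0 | 0.5 | 1.5 | 2.8 |
| 4 | 1 patient | 0.3 | 1.1 | 2.1 |
| 4 | 2 patients | 0.2 | 0.7 | 1.5 |
| 5 | 0 | 0.1 | 0.6 | 1.4 |
| 5 | 1 patient | 0.1 | 0.3 | 1.0 |
| 5 | 2 patients | 0.04 | 0.2 | 0.6 |

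The chance that the count is reached before patient 12 is 16.1/43.0/70.4% for r = 4 and 5.0/21.0/46.7% for r = 5.

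**Step 4: calendar time.** Three per quarter at 1:1 is 1.5 per quarter on the investigational arm. Twelve patients then take 12 / 1.5 = 8 quarters, about two years, or one patient every two months. SAE reports due within 24 hours would normally arrive well before the next patient, so counting events as they occur is practical.

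**The case against.** - **The stop sentence carries no timing condition.** It can be read as already satisfied once the count is reached, with the sentence before it only scheduling an analysis. This stands. A reader might infer that the protocol requires enrollment to continue after the boundary is met; the text does not say so. The gap is that no trigger is stated, not that continuation is ordered.
- **Other oversight exists.** Ongoing DSMB review, monthly internal review, monthly site calls and 24-hour SAE reports make it unlikely that a run of related Grade 3 or higher SAEs would go unnoticed. This also stands, and the charter, where DSMB processes are to be set out, is not part of the documents. Given a stop with r = 4, the count is reached on average at patient 9.1 (p = 30%) or 8.4 (p = 40%). A reader might turn the remaining 2.9 or 3.7 patients, at 1.5 per quarter, into two quarters or more of further dosing. That figure is conditional on stopping, assumes zero lag in the comparison, and assumes that nobody acts under the discretionary routes. The unconditional figures are the fair measure.
- **The boundary is unsettled.** A reader might infer that the fourth event makes the stop certain. That holds only for the written boundary. If the printed probabilities reflect the intended rule, it is the fifth event. The timing argument survives for either count, but no number can be fixed in the text until the two are reconciled.
- **The benefit is negligible if the agent is well tolerated.** D-1.2.1.8 reports at most 5 subjects with a possibly related Grade 3 SAE; against the 72 in Table D-1 that is about 7%, mostly at other doses or schedules. At that rate boundary 4 is reached in under 1% of trials and about 0.01 patient is spared. This is true, but the rule exists for the case where toxicity is worse than expected.
- **Rule 2 is not a full parallel.** It halts enrollment pending review, whereas rule 1 stops the study. It shows only that the plan can act on a count when it is reached.

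**Conclusion.** The point holds as a modest safety improvement at almost no cost. Rule 1 has a boundary that cannot reverse and a formal look tied to the 12th randomization, and everything that could act earlier is discretionary. Acting when the count is reached leaves the stopping probability exactly unchanged for whichever boundary is chosen. With no lag, the average saving per investigational arm at true rates of 20% to 40% is 0.5 to 2.8 patients for boundary 4 and 0.1 to 1.4 for boundary 5; recognition lag reduces it but does not remove it. These sizes assume independent patients, a constant rate and no earlier discretionary action.

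An unchanged stopping probability means unchanged for a given boundary. It does not mean that the printed 7/28/56% apply to the rule as written; they do not.

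**What to change.** 1. Reconcile the written boundary (four or more of 12) with the printed stopping probabilities (which belong to five or more of 12). This review does not say which is right.
2. Then add one sentence to Section 12.2: the rule's consequence, exactly as the protocol already words it, takes effect as soon as the reconciled number of qualifying toxicities is reached among the first 12 patients on an investigational arm; otherwise the formal DSMB review takes place at 12. The wording should not narrow or widen that consequence.
3. Name the existing 24-hour SAE reports (Sections 7.5 and 7.5.1) as the trigger, and put a matching line in the DSMB charter.

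The cost is one sentence and one charter line. No extra data, visits or patients are needed, and the stopping probability for the chosen boundary does not change.
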